### 4.2. Exclusion Criteria

Patients must meet all the inclusion criteria listed above and none of the following exclusion criteria:

- a) Prior treatment with an anti-ErbB3 antibody
- b) Prior treatment with a chemotherapy in the locally advanced or metastatic disease setting
- c) Patients cannot have received prior treatment with fulvestrant or other SERDs in the locally advanced or metastatic setting
- d) Uncontrolled CNS disease or presence of leptomeningeal disease
- e) Inflammatory breast cancer
- f) History of another active malignancy that required systemic therapy in the last 2 years. Patients with prior history of in-situ cancer or basal or squamous cell skin cancer are eligible
- g) Active infection, or an unexplained fever > 38.5°C during screening visits or on the first scheduled day of dosing, which in the investigator's opinion might compromise the patient's participation in the trial or affect the study outcome. At the discretion of the investigator, patients with tumor fever may be enrolled
- h) Known hypersensitivity to any of the components of seribantumab, fulvestrant, or who have had hypersensitivity reactions to fully human monoclonal antibodies
- i) Received other recent antitumor therapy including:
  - Investigational therapy administered within the 28 days or 5 half-lives, whichever is shorter, prior to the first scheduled day of dosing in this study
  - Radiation or other standard systemic therapy within 14 days prior to the first scheduled dose in this study, including, in addition (if necessary), the timeframe for resolution of any actual or anticipated toxicities from such radiation
- i) NYHA Class III or IV congestive heart failure
- k) Patients with a significant history of cardiac disease (i.e. uncontrolled blood pressure, unstable angina, myocardial infarction within 1 year or ventricular arrhythmias requiring medication) are also excluded

- 1) Uncontrolled infection requiring IV antibiotics, antivirals, or antifungals; or active human immunodeficiency virus (HIV) infection, active hepatitis B infection or active hepatitis C infection
- m) Any other medical condition deemed by the Investigator to be likely to interfere with a patient's ability to sign informed consent, interfere with a patient's ability to cooperate and participate in the study, or interfere with the interpretation of the results

### 4.3. Assessing Heregulin Status in Breast Cancer Specimens

This study will only enroll patients with HRG positive tumors (defined as tumors with a HRG RNA-ISH score of ≥1+). Patients presenting with HRG negative tumors (HRG ISH score of 0) will not undergo any additional study procedures and will be considered screen failures; however, some minimal medical history information will be collected. A patient's tumor HRG status will be assessed at a central CLIA certified lab using a qualified RNA in situ hybridization (ISH) assay.

# 4.3.1. Description of HRG RNA-ISH Assay

RNA-ISH is a test in which oligonucleotide target probes are hybridized to the RNA in formalin-fixed, paraffin-embedded (FFPE) tissue samples. The signal on the target RNA molecule is detected by using a chromogenic substrate reaction. This approach enables mRNA molecules to be visualized and scored by pathologists in a manner similar to a standard immunohistochemistry (IHC) assay.

## 4.3.2. Implementation of HRG RNA-ISH Testing

The HRG RNA-ISH assay can be used to measure mRNA expression on tissue slides obtained from formalin-fixed paraffin embedded archived blocks, core biopsies or fine needle aspirates; therefore, any of these methods of collection is acceptable for testing. Formalin-fixed clinical trial specimens will be submitted directly by clinical sites to the designated CLIA certified central lab. Full details regarding collection, processing and shipment of samples are outlined within the study lab manual.

The central lab will process the samples and provide the stained slides to a trained pathologist to assess tumor content and percentage of tumor cells expressing HRG mRNA. The pathologist will assign scores of 0, 1+, 2+, or 3+ based on HRG mRNA staining. Samples scored at  $\geq$  1+ will be considered HRG positive, and samples scored at 0 will be considered HRG negative. This result will be communicated back to the investigative site within 7 days of sample receipt at the central lab.

#### 4.4. Patient Discontinuation

A patient may withdraw from the study at any time and for any reason. It is intended that patients will be treated until investigator-determined progressive disease (radiologic or clinical deterioration) or unacceptable toxicity. Some possible reasons for withdrawal from treatment include, but are not limited to the following:

- Progressive neoplastic disease per RECIST v1.1
- Clinical deterioration
- Adverse event, including treatment being withheld for 21 consecutive days without resolution of toxicities to grade 1 or baseline value

- Protocol violation / non-compliance
- Withdrawal of consent
- Investigator or sponsor decision
- Patient is lost to follow-up

When a patient is discontinued from treatment for any reason, they are to undergo the assessments in the End of Treatment visit within 30 days of the last dose. All patients who discontinue treatment as a result of an adverse event must be followed until resolution or stabilization of the adverse event. At the time a patient withdraws from study treatment, an attempt should be made to determine the reason(s) for discontinuation. The patient will continue to be followed for survival information every 2 months after completion of the End of Treatment visit. All patients, including patients who discontinue treatment for reasons other than progressive disease per RECIST 1.1, should undergo a scan to assess disease status at the time of treatment discontinuation, and again 8 weeks following treatment termination.

If a patient does not return to the clinic for the end of treatment visit or is not reached for overall survival follow-up, at least 3 documented attempts, including one via certified mail, should be made to contact the patient. If there is no response to these requests, the date of death should be captured from public records.

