## 5.2.5. Management of Toxicity Related to Seribantumab

In the event that a patient experiences a toxicity  $\geq$  Grade 3 that is not an IRR and is possibly, probably or definitively related to seribantumab treatment, and not related to fulvestrant, it is at the investigator's discretion to hold dosing or discontinue treatment with seribantumab. Prior to holding the dose or discontinuing treatment, the investigator must notify the sponsor and Medical Monitor.

In the event that seribantumab treatment has been held for 28 consecutive days, the patient should be discontinued. No dose reductions for seribantumab are permitted.

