#### 5.4. Rules for Dose Omissions and Modified Treatment Schedules

It is intended that seribantumab and fulvestrant dosing occur on schedule per the protocol. In the event that dosing of any study drug has been held for 28 consecutive days and the investigator does not wish to continue dosing, the patient should be discontinued from treatment.

Dose modifications of seribantumab are not allowed. Any dose modifications to fulvestrant should be performed in line with the local package insert, and should be discussed and approved by the Sponsor prior to implementation.

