## **3. ENDPOINTS**

## 3.1 Progression-Free Survival – Investigator Assessed

Investigator Assessed (IA) tumors assessments are those determined by the investigator. PFS is defined as the number of months from the date of randomization to the date of death or documented (objective) disease progression via RECISTv1.1, whichever occurs earliest. Length of PFS will be calculated in days and reported in months.

[Progression/Death/Censor Date - Randomization Date + 1] / 30.4375.

The tumor assessment (i.e., scan dates) will be used for progression/censor date not the date corresponding to the determination of overall response. When multiple dates occur for assessing target, non-target, and new lesions the following rule will be applied:

- If documented disease progressions, the *first* available date will define the tumor assessment date
- If censored, the *last* available date will define the tumor assessment date.

Per protocol tumor assessments are scheduled to be performed every 8 weeks ( $\pm$  7 days) from day of first dose until investigator-assessed progression, in addition to a 30-day follow-up.

**Censorship**: In general, patients are censored at the date of the last tumor assessment that verified lack of disease progression if they are last known to be alive, on-treatment or within 30 days following treatment discontinuation, and progression-free. Censoring is explicitly described below and in table 1. Patients that do not experience progression or death by the time of analysis (data cut-off) will be censored at the date of last tumor assessment defined by any overall response other than "not evaluable".

- Patients with an inadequate/incomplete baseline tumor assessment will be censored at the date of randomization
- Patients with no tumor assessment after dosing will be censored at the date of randomization unless death occurred prior to the first planned assessment (in which case the death is an event)
- Patients with at least one on-study disease assessment who discontinue treatment without documented disease progression or death are censored at the date of the last tumor assessment

There are two exceptions.

- $\circ$  Documented progression or death  $\leq$  30 days after treatment discontinuation then progression or death is an event

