#### Table 3.1 Documented Disease Progression and Censoring

Situation	Date of	Outcome
Inadequate baseline tumor assessment No on-treatment assessment and no death prior to first scheduled assessment	Randomization	Censored
Death or documented disease progression after ≥ 2 consecutively missed and/or not evaluable scheduled tumor assessments	Last tumor assessment documenting no disease progression	Censored
Alive, on-treatment, and no documented disease progression	Last tumor assessment documenting no disease progression	
Documented disease progression (on, prior to, or $\leq 30$ days after treatment discontinuation)	First tumor assessment documenting disease progression	Progression (Event)
New anticancer treatment $\leq$ 30 days after treatment discontinuation without disease progression	Last tumor assessment documenting no disease progression prior to starting the new anticancer treatment	Censored
Treatment discontinuation due to toxicity, undocumented disease progression, or any other reason	Last tumor assessment documenting no disease progression prior to discontinuation	Censored
Death prior to first scheduled assessment	Death	Death (Event)
Death without documented disease progression and $\leq 30$ days after treatment discontinuation	Death	Death (Event)

Note: Follow-up scans can be performed up to 4 weeks from last treatment dose date via protocol

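### Protocol sections 5.2.5 and 5.4 disagree on whether a 28-day seribantumab hold ends treatment when the investigator wishes to continue, and section 4.4 adds an unexplained 21-day figure

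*Protocol*

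**What the plan says.** Three protocol sections speak to how long treatment may be held.

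- Section 5.2.5, on seribantumab toxicity: "In the event that seribantumab treatment has been held for 28 consecutive days, the patient should be discontinued". No further condition is attached.
- Section 5.4, on dose omissions for both drugs: the patient should come off treatment if "dosing of any study drug has been held for 28 consecutive days and the investigator does not wish to continue dosing".
- Section 4.4, on patient discontinuation: under adverse events it names "treatment being withheld for 21 consecutive days without resolution of toxicities to grade 1 or baseline value". The list containing this item opens with "Some possible reasons for withdrawal from treatment include, but are not limited to the following".

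The SAP makes stopping treatment relevant to PFS. Its section 3.1 states that patients with at least one on-study assessment "who discontinue treatment without documented disease progression or death are censored at the date of the last tumor assessment". An exception keeps progression or death as an event if it falls within 30 days of stopping. Table 3.1 has a matching censoring row: "Treatment discontinuation due to toxicity, undocumented disease progression, or any other reason".

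**The concern.** A site whose patient has reached day 28 of a seribantumab hold, and whose investigator wants to resume, finds an instruction to discontinue in one section. In another section, the condition for discontinuing is not met. A third section gives a shorter duration with no explanation of how it relates to the other two. Different sites could reasonably act differently on the same patient.

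What is at stake is first the consistent handling of patients with toxicity, across an estimated 60 to 80 sites. Discontinuation also starts other procedures: section 4.4 calls for a scan when treatment stops, another 8 weeks later, and the End of Treatment assessments. If the stopping rule is read differently, these are triggered in different patients and at different times. A secondary question is whether the stop date could also alter who counts as a PFS event.

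**Working it through.** No figure in the plan is disputed here. For completeness, the 58 events reproduce with the Schoenfeld formula: 4 × (1.2816 + 0.8416)² / (ln 0.57)² = 18.03 / 0.316 = 57.1, rounded up to 58. This point does not touch that number. The check is a comparison of the three sections.

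**1. A seribantumab hold, by duration and circumstance**

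| Situation | 4.4 | 5.2.5 | 5.4 |
|---|---|---|---|
| Days 21 to 27, toxicity unresolved | Possible reason to withdraw | 28-day trigger not reached | 28-day trigger not reached |
| Day 28, investigator does not wish to continue | Possible reason if toxicity unresolved | Discontinue | Discontinue |
| Day 28, investigator wishes to continue | Possible reason if toxicity unresolved | Discontinue | Condition for discontinuing not met |

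The last row is the inconsistency. Section 5.4 covers seribantumab: it opens by naming both drugs and applies to any study drug.

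The first row is a gap in explanation. The two thresholds differ by 28 − 21 = 7 days. The 21-day item depends on unresolved toxicity and the 28-day items do not. No section says how they fit together.

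**2. Which drug stops**

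Section 5.2.5 first lets the investigator hold or stop seribantumab, then speaks of discontinuing the patient without saying from what. Section 5.4 speaks of coming off treatment. Section 5.2.4, on Grade 3 and 4 infusion reactions, bars further seribantumab specifically. The protocol is therefore drug-specific in some places, and 5.2.5 does not say whether fulvestrant continues.

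**3. Where the count starts**

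The start of a hold is not defined. Seribantumab is given 14 days apart.

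- Counted from the last dose given, holds of 21 and 28 days both end within 30 days of that dose.
- Counted from the first omitted dose, they end 14 + 21 = 35 and 14 + 28 = 42 days after it.

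Sections 4.4 and 6.5 place the End of Treatment visit within 30 days of the last dose. Section 3.1 allows 30 ± 7 days, which covers 35 but not 42. So the visit window may have closed before the hold rule applies. This assumes that no other study drug was given during the hold.

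**4. The link to PFS**

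- Under the SAP, stopping without progression censors at the last assessment, subject to the exception "30 days after treatment discontinuation then progression or death is an event", where the limit is 30 days or fewer. The stop date can therefore matter.
- Under the protocol synopsis, it does not. Censoring there follows a new anti-cancer treatment, two or more missed or indeterminate assessments, no valid baseline evaluation, or no event. Sections 3.1 and 7.7 continue 8-weekly scans after treatment stops, until progression.
- Protocol section 10.5.1 leaves censoring detail to the SAP. The SAP supplied names protocol 02-03-10, not MM-121-02-02-10. It describes a phase 3 trial of exemestane or fulvestrant with 2:1 allocation, 286 patients and 195 events. This protocol has 1:1 allocation, 80 patients and 58 events.

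**The case against.** The best defence is that the sections can be read together. Section 5.2.5 is the specific provision for seribantumab toxicity and 5.4 the general one. Section 5.4 gives one case in which treatment stops and does not say that this is the only case. Both use advisory wording. Section 5.2.5 requires the sponsor and Medical Monitor to be told before a dose is held, so difficult cases can be settled centrally. The 21-day item is an example in an open list, and stopping earlier than day 28 is compatible with a 28-day limit. Sections 5.2.5 and 5.4 both speak of discontinuing the patient, which suggests that all treatment stops.

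Much of this stands. A reader might infer three competing mandatory rules, but section 4.4 does not support that: its item is a possible reason, not an instruction. A reader might also infer that 5.4 permits a hold of unlimited length. It sets no maximum, but nor does it say that treatment may continue indefinitely.

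The defence does not remove the 28-day conflict. Neither section cites the other or states which prevails, so giving precedence to the specific section is the reader's own rule. Notifying the sponsor before a hold does not tell a site what applies at day 28. The patient-level wording in 5.2.5 follows a sentence about stopping seribantumab alone, so the question of which drug stops is only partly answered.

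**Conclusion.** The concern holds as an internal inconsistency in the protocol, confined to one situation: a seribantumab hold that reaches 28 days while the investigator wishes to continue. The 21-day figure and the unstated drug coverage are ambiguities that add to it. The wording should be corrected because it governs patients with toxicity and the procedures that follow discontinuation. The number of patients affected cannot be estimated, because the documents give no frequency of holds in this trial.

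Two stronger readings are tempting and are not supported.

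- A reader might infer that the 7-day difference moves a calculable set of progressions across the SAP's 30-day limit. That requires the stop date to be the date of the decision, which the SAP does not define. Nearby SAP text (the note to Table 3.1 and section 5.4.1) counts from the last dose. On that basis a patient who never resumes has the same date under either threshold, and the shift is zero. The rules would still affect who may resume.
- A reader might infer that the effect falls mainly on the arm with more toxicity. No document gives hold rates by arm.

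Any PFS effect is therefore secondary and conditional on the supplied SAP. That SAP's stop-date censoring conflicts with this protocol's PFS rule. Aligning the hold rules would not resolve that separate conflict. No sample size or power figure changes.

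**What to change.** Reconcile protocol sections 4.4, 5.2.5 and 5.4 into one consistent statement that gives:

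- the hold duration and the day from which it is counted;
- whether stopping is mandatory or at the investigator's discretion, and whether resolution of toxicity matters;
- which drug or drugs the rule covers.

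State it once and cross-refer to it from the other sections. The sponsor's clinical team decides the content; this review takes no position on which rule is right.

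Separately, the SAP's censoring on treatment discontinuation and the protocol's PFS rule should be aligned, and the discontinuation date defined wherever the analysis uses it.

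The hold rules need only a wording change in a protocol amendment, with no added visits or patients. The PFS alignment is an edit to the analysis plan.

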# 5. Study Treatment

### 5.1. Method of Assigning Patients to Treatment Groups

If a patient is determined to be HRG positive, investigators will determine whether all other study enrollment criteria have been fulfilled. Upon completion of screening assessments, eligible, patients will be randomized 1:1 to the treatment or control arm using an Interactive Web Response System (IWRS). Randomization will be stratified based on bone-only disease (yes, no) and geographic status (US, non-US).

### 5.2. Seribantumab

### 5.2.1. Seribantumab Formulation, Packaging, and Labeling

Seribantumab is supplied for IV administration as a sterile, colorless liquid at 25 mg/mL. It is packaged in sterile, single-use, clear borosilicate Type 1 glass vials that are closed with a coated rubber stopper and flip-off cap with flange.

Multiple vials of seribantumab will be packaged in a cardboard container. The individual vials, as well as the outside of the cardboard container, will be labeled in accordance with regulatory requirements and in compliance with country-specific guidelines. Additional details are provided in the study pharmacy binder.

# 5.2.2. Seribantumab Product Storage and Stability

Seribantumab Drug Product must be stored refrigerated (2-8°C) with protection from light. Light protection is not required during preparation or infusion. Seribantumab must not be frozen.

Based on available stability data, the concentrate for solution for infusion is stable for at least 36 months when stored according to conditions specified in the clinical supply label. Continued stability data are being generated, and longer stability may be available during the course of the

study. The date of expiration will be noted on the drug label, or via other pharmacy notifications as required by local regulation. Seribantumab should not be used beyond the date of expiration.

### 5.2.3. Seribantumab Dosage, Preparation, and Administration

Seribantumab should be administered as an IV infusion at a fixed dose of 3000 mg on day 1 and day 15 of each 28-day cycle.

Administration of seribantumab will require multiple vials, all of which should come from the same lot number. Seribantumab should be brought to room temperature prior to mixing with saline. Vials of seribantumab should not be shaken. The appropriate quantity of study drug will be removed from the vial, diluted with 0.9% normal saline to a final volume of 250 ml and administered over 60 minutes (±15 minutes) for all infusions in the absence of infusion reactions, using a low protein binding 0.22 micrometer in-line filter. The equivalent amount of saline should be removed from the infusion bag to fill with seribantumab to 250 ml. The line should be flushed before and after the study drug infusion. Study drug should not be administered as a bolus or a push.

#### 5.2.4. Management of Infusion Reactions to Seribantumab

Like other IV infusions, seribantumab administration may be associated with infusion related reactions (IRRs). Infusion related reactions will be defined according to the National Cancer Institute CTCAE (Version 4.03) definition of an allergic reaction/infusion reaction and anaphylaxis. In past clinical studies, IRRs with seribantumab have been rare with < 1% of patients reporting an IRR, of which all were Grade 1 or 2. Study site policies or the following treatment guidelines shall be used for the management of infusion reactions.

### Grade 1

- Slow infusion rate by 50%
- Monitor patient every 15 minutes for worsening of condition

#### Grade 2

- Stop infusion
- Administer diphenhydramine hydrochloride 50 mg IV, acetaminophen 500-650 mg orally or IV, and oxygen
- Resume infusion at 50% of the prior rate once infusion reaction has resolved
- Monitor patient every 15 minutes for worsening of condition
- For all subsequent infusions, pre-medicate with dexamethasone 10 mg orally or IV

# Grade 3

- Stop infusion and disconnect infusion tubing from patient
- Administer diphenhydramine hydrochloride 50 mg IV, dexamethasone 10 mg IV, bronchodilators for bronchospasm, and other medications or oxygen as medically necessary
- No further treatment with seribantumab will be permitted

#### Grade 4

- Stop the infusion and disconnect infusion tubing from patient
- Administer epinephrine, bronchodilators or oxygen as indicated for bronchospasm

- Administer diphenhydramine hydrochloride 50 mg IV, dexamethasone 10 mg IV
- Consider hospital admission for observation
- No further treatment with seribantumab will be permitted

For patients who experience a Grade 1 or Grade 2 infusion reaction, at the discretion of the investigator, future infusions may be administered at a reduced rate (over 90 minutes).

For patients who experience a second Grade 1 or 2 infusion reaction, administer dexamethasone 10 mg IV. All subsequent infusions should be pre-medicated with diphenhydramine hydrochloride 50 mg IV, dexamethasone 10 mg IV, and acetaminophen 500-650 mg orally.

For patients who experience a Grade 3 or 4 infusion reaction, an anti-seribantumab antibody titer will be taken as close to the onset of the infusion reaction as possible for any patient experiencing an infusion reaction to seribantumab. Anti-seribantumab antibody titer should also be obtained at the resolution of the event and 28 days (+/- 2 days) following the event.

